The combined use of these lasers represents a novel approach to addressing diverse skin care goals. To our knowledge, this is the first study to investigate the combined effects of these three modalities on skin rejuvenation and overall skin health in a single setting.

Device	Characteristics	Wavelength	Target	Previous Studies
BBL Broad based light (BBL HERO)	IPL Nonablative		Freckles Age Spots Cherry Angiomas Rosacea Dull complexion Acne Skin Laxity Unwanted hair	Berlin et al 2007 Siperstein et al 2021 Handler et al 2017
MOXI	Fractionated thulium Nonablative (1927 nm laser)		Pigmentation Sun damage (UV spots) Signs of aging (brown spots)	Vingan et al . 2023 Li et al 2023
HALO	Dual fractionated hybrid laser Non-ablative (1470 nm) & Ablative (2940 nm)		Fine lines & Wrinkles Sun damage & dyschromia Scar revision Pigmented lesions Enlarged pores	Kislevitz et al 2020 Waibel et al 2018

Purpose

This single-site clinical trial is being conducted over the course of 4 to 6 months. Healthy subjects will receive 1-2 treatments combining BBL/MOXI/HALO during this trial and be followed up 1 month and 3 months after their final treatment to assess noted changes.

The primary objective of the study is to assess the efficacy of this BBL/MOXI/HALO combination treatment.

Project Summary

Clinical Study

This is a single-site, non-randomized, non-controlled study at UT Southwestern Medical Center at Dallas in the Department of Plastic Surgery. The study is designed to follow up to 15 consenting subjects who may receive up to 2 BBL/MOXI/HALO treatments under an IRB approved protocol. The BBL/MOXI/Halo treatments are all within the Joule System and is used as separate or combination treatments as part of standard of care within the clinic.

The Principal Investigator (PI) has been selected based on expertise, qualifications, previous clinical research and interest in this field of research. Subjects will be identified and recruited from the clinic of plastic surgery at UT Southwestern Medical Center.

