Subjects will be consented by a member of the research team and subjects will be numbered in the order that consent is obtained, and all assessments and documents will contain the assigned ID for the duration of the study. Subjects will receive 1-2 BBL/MOXI/HALO treatments. All 2nd treatments will be scheduled 4-8 weeks after the initial treatment to ensure the skin has enough time to recover. Overall assessments will be collected before the first treatment and at subsequent follow-up visits at 1 Month and 3 Months post final treatment. Identifiable full-face standard and close-up photography will be obtained and used to evaluate any changes. Subjects will also have photos obtained with the VISIA-CR Imaging System (Canfield Scientific, Parsippany, NJ). Quantitative analysis will be completed on the VISIA imaging system and be used to compare the effects of the treatments. Any improvements will be evaluated to pre-treatment assessments.

Primary Endpoints

Assessment of changes by VISIA Imaging System of photos obtained pre-treatment, 1 Month and 3 Months post-treatment.

- Calculate percent change from baseline in numeric analysis via the VISIA Imaging System
 - VISIA- CR Imaging system will be utilized to capture qualitative and quantitative data including, but not limited to: spots, wrinkles, texture, pores, UV spots, brown spots, red areas and porphyrins.
 - Clinician assessment of improvement using the Global Aesthetic Improvement Scale.

Secondary Endpoint

Monitor incidence, severity and relatedness of adverse events throughout the study.

Study Device Information

	Proprietary Information	Device Description	Regulatory Information
Device Name:	Sciton BBL HERO	Aesthetic device utilizing broadband light to improve the appearance of aging, reduces rosacea, acne, melasma and sun spots	
JOULE Multi-Platform System	Sciton MOXI	Aesthetic laser device that utilizes a fractionated laser to treat uneven pigmentation and heal photodamage skin	Class II 510(K) Number: N/A Regulation number: 878.4810
	Sciton HALO	Aesthetic laser device that utilizes a hybrid fractionated laser to treat fine lines & wrinkles and reduce the appearance of enlarged pores, sun damage and dyschromia	

Study Population & Enrollment

Enrollment

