After the procedure, subjects will be provided appropriate post-treatment care instructions as deemed appropriate by the Investigator or study staff. Subjects will be instructed that blistering, bleeding, oozing, strong pain, swelling persisting for more than 72 hours, or signs of infection (e.g., pus, drainage, fever) are cause for immediate concern and they should contact the investigator and/or his designee, to be evaluated. Expected downtime after BBL/MOXI/HALO is expected to be 7-10 days.

The treatment visit(s) is expected to take approximately 1 hour.

*A subset of subjects will return for a second treatment 45-60 days after the initial treatment. The PI and/or Sponsor will make a determination if a second treatment would be beneficial to the subject. All follow up visits will be scheduled accordingly.

PI Assessment: Visit 3 (1-month follow-up from initial treatment)

The physician will assess the patient at their 1-month follow-up after the initial treatment. The treating physician will determine if a single treatment is sufficient for achieving aesthetic goals or a second treatment is indicated based on the patient's presentation. Candidacy for a second treatment may involve assessment of the following factors:

- Stage of healing
- Absence of complications and adverse events
- Treatment tolerance by patient
- Patient interest and consent
- Review of VISIA data and Photography

Follow Up Visits (1M & 3M post final treatment): Visit 3 & 4 (Single tx) or Visit 5 & 6 (Double tx)

At a minimum, all subjects will return for follow-up visits at 1 month (\pm 7 days) and 3 months (\pm 7 days) after the final treatment.

The following activities will be performed on all study subjects during the follow-up visits:

1. The physician or study staff will ask subjects if they have experienced any changes in their health since the previous visit. Changes will be recorded accordingly. If an adverse event (AE) is reported then the Investigator will be informed, and an AE form will be completed.
2. Subjects will acclimate to ambient temperature and humidity conditions for 15 minutes prior to any procedures being done.
3. The physician or study staff will perform an examination of the skin in the treatment area
4. Obtain post-treatment close-range and standard photography as described in section entitled, "Assessments", for research purposes.

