5. Obtain post-treatment photographs and measurements using the Vectra H2 3D Imaging System and VISIA Imaging System as described in section entitled, "Assessments", for research purposes.

These visits will take about 30 minutes.

Assessments

Photography Procedures

NIKON D7200

Standard and close-range of the face will be utilized for evaluation of pigmentation. These photographs will be taken utilizing the Nikon D7200 at Baseline (Screening Visit), 1-month post-treatment and 3-months post-treatment.

VISIA CR Imaging System

Subjects will be instructed to adopt neutral, non-smiling expressions for each photograph. Images will be taken of each applicable subject with diffuse pigmentation of the face using the Vectra H2 3D Imaging System at Baseline, 1-month post-treatment and 3-months post-treatment. Each subject will have a total of 3 photos taken (right side, left side and center view).

Potential Risks

Risks of Anesthetic

Allergic Reaction (Rare)

There is a possibility of an allergic or toxic reaction to anesthesia used to numb the areas. Subjects will be questioned with regard to any history of allergies and carefully monitored for signs of allergic reaction.

Risks of Treatments

BBL: Broad Band Light

Erythema: (Occasionally < 3%)

May develop within the irradiated areas but are usually temporary and fade within 24-72 hours. There is a 90% chance of transient edema and 99% chance of erythema to occur after treatment.

Swelling and/or itching: (Occasional <3%)

May occur in the area of treatment and may last up to several hours. The pattern of the treatment may be visible on the skin, but this usually fades with healing. Itching and hive-like appearance may also occur.

Bruising: (Rare < 1%)

A mild bruising may occur at the treatment area as a result of laser exposure. This is usually transient and resolves in a few hours to few days.

Skin roughness and/or peeling (Occasional <3%)

Patients can expect their treated skin to feel rough like sandpaper for a few days while the skin heals. This is transient and should resolve in a few days.

Lasers: MOXI (Non-ablative Laser Facial Resurfacing & HALO (Fractionated Laser)

Blistering, burning, scaling and infection: Rare < 1%)

A crust, blister or superficial wound can occur at the treatment area. The risk of infection will be minimized by proper wound care.

Bruising: (Rare < 1%)

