A mild bruising may occur at the treatment area as a result of laser exposure. This is usually transient and resolves in a few hours to few days.

Transient edema and/or erythema: (Occasionally < 3%)

May develop within the irradiated areas but are usually temporary and fade within 24-72 hours. There is a 90% chance of transient edema and 99% chance of erythema to occur after treatment.

Pigmentary changes: (Rare < 1%)

Laser exposure can cause pigmentary changes such as hyper- (3% chance) and hypo-pigmentation (<.5% chance). Although this is usually temporary, it may be permanent on rare occasions. Sun avoidance and/or the use of a total sun block (SPF 30 or higher) will help minimize the intensity and duration of any pigmentary changes.

Skin roughness and/or peeling (Occasional <3%)

Patients can expect their treated skin to feel rough like sandpaper for a few days while the skin heals. This is transient and should resolve in a few days.

Eye injury: (Rare < 1%)

There is a risk of eye injury associated with the use of this device. This risk will be minimized by wearing protective eyewear designated for use with this device. All subjects and other personnel must use proper protective eyewear during the use of this device.

Scarring: (Rare < 1%)

As with any form of laser exposure, there is a small risk of scarring. However, this is minimized by proper technique and wound care.

Risks of Photography:

The subject may be uncomfortable with sitting still for an extended period of time or from turning his/her body in various positions. Subjects may be sensitive to bright and repeating flashes from the camera, which can sometimes cause headaches, eye irritation, discomfort, aftereffects such as seeing spots, and in rare cases, could stimulate a migraine headache or epileptic seizure.

Photographs include a risk of identification, as these will be full face photos. Privacy will be protected to the greatest extent possible. Photos will only be identified by unique subject identification number that contains no personal

identifying information. All photos will be stored on a password secure drive, with only access by research personnel. For research purposes, photos may be used in scientific publications.

Adverse Events

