At each visit, a member of the research team will question the subject about adverse events using an open-ended question. If a potential adverse event is reported by the subject or identified during examination, directed questioning and examination will be performed when appropriate. At this time, the following will be performed:

1. Obtain a complete history of the event in question as well as conduct an examination of the subject and determine if the reported event qualifies as an Adverse Event (AE). If the event is determined to be an AE, an AE case report form and Event Follow-up (EF) visit case report form must be completed. One AE case report form should be used to track the history of an individual AE throughout the period of the study.
2. Collect an updated medical and surgical history along with recording of concomitant medications or treatments.
3. Take photographs of the subject with attention to the area in question.
4. Render treatment for the event, if any, as determined by the medical judgement of the Investigator.

Photographs will be taken to document any AEs if possible.

For the duration of the study, medical assistance will be provided to the subject for study-related problems at no expense, if in the opinion of the Investigator, the reaction was caused by BBL/MOXI/HALO treatments. Should a subject choose to seek their own medical treatment, no reimbursement will be offered.

When an AE persists at the end of the study, the Investigator will ensure a follow-up of the subject until the Investigator believes that the event is satisfactorily resolved.

Subject Safety & Data Monitoring

Research Standards and Good Clinical Practice

The conduct of this study will follow all applicable guidelines for the protection of human subjects for research as outlined in 21 CFR 50, in accordance with the accepted standards for Good Clinical Practice (GCP), International Conference on Harmonization (ICH), and the standard practices of UT Southwestern.

Data Monitoring

For this protocol, which involves the use of a non-significant risk device, the Investigator will monitor accrual, subject experience, attrition, patterns of adverse events and/or unexpected adverse events, any protocol deviations, or violations any changes in the risk/benefit analysis.

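### The plan does not define an adverse event or say whether near-universal expected reactions count, and its form triggers differ, so adverse-event incidence cannot be interpreted as written

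*Combined protocol and SAP*

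**What the plan says.** The Secondary Endpoint section has one item: "Monitor incidence, severity and relatedness of adverse events throughout the study". Under Clinical Study, the size is given as "The study is designed to follow up to 15 consenting subjects", in a single-site study with no control group.

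Three places say when an event reaches a form:

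- **Adverse Events, step 1.** Subjects are asked an open-ended question at each visit. For a potential event, staff take a history, examine the subject and "determine if the reported event qualifies as an Adverse Event (AE". Then: "If the event is determined to be an AE, an AE case report form and Event Follow-up (EF) visit case report form must be completed". The section gives no criteria for qualifying and does not say who decides.
- **Study Visits, treatment visits.** A log is completed or updated when an adverse event is reported. No qualifying step is mentioned.
- **Study Visits, follow-up visits.** A form is completed when an adverse event is reported. Again no qualifying step is mentioned.

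Under Risks of Treatments, both the BBL part and the MOXI/HALO part state: "There is a 90% chance of transient edema and 99% chance of erythema to occur after treatment". In each part that sentence stands under a heading that labels the reaction as occurring in fewer than 3%. The same text says these reactions usually fade within 24 to 72 hours.

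The Visit 3 assessment lists "Absence of complications and adverse events" among the factors that may be considered for a second treatment. The Statistical Analysis section has no adverse-event analysis and restricts analysis to subjects who complete the study.

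**The concern.** An incidence needs a fixed rule for what enters the numerator. Here the rule is a case-by-case decision without criteria. By the protocol's own descriptive text, the reactions it would most often be applied to occur in nearly every subject. Two careful teams could follow the protocol faithfully and report very different rates from the same subjects.

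The stakes are higher because there is no control arm to put the count in context, and the protocol describes the study as the first of the three devices combined in one setting. A reader who sees a low rate could not tell whether the treatment was well tolerated or the definition was narrow. A reader who sees a rate near 100% could not tell whether it reflects more than expected redness.

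**Working it through.** The documents contain no adverse-event calculation to reproduce. The 99% and 90% are stated inputs, and no calculation supports the 15 subjects. The check is how far incidence moves when only the definition changes.

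**Inputs** (n = 15 from Clinical Study; the rest from Risks of Treatments)

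| Reaction | Value used |
|---|---|
| Erythema | 99% |
| Transient edema | 90% |
| Blistering, burning, scaling, infection | 1% (upper) |
| Bruising (listed twice, counted once) | 1% (upper) |
| Hyperpigmentation | 3% |
| Hypopigmentation | 0.5% (upper) |
| Eye injury | 1% (upper) |
| Scarring | 1% (upper) |
| Swelling and/or itching | 3% (upper) |
| Roughness and/or peeling | 3% (upper) |

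Anesthetic allergy is listed as rare without a figure and is left out.

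**A. Expected reactions count**

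- Expected with erythema: 15 × 0.99 = 14.85. Expected with edema: 15 × 0.90 = 13.5.
- P(all 15 have erythema) = 0.99^15 = 0.860.
- P(at least 14) = 0.99^15 + 15 × 0.01 × 0.99^14 = 0.990.
- Any-event incidence is therefore about 14 to 15 of 15.

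**B. Expected reactions do not count** (one treatment, independent risks)

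- Erythema and edema contribute 0.
- Without itching and roughness, the sum of the other risks is 0.01 + 0.01 + 0.03 + 0.005 + 0.01 + 0.01 = 7.5%. Under independence, 1 − 0.99^4 × 0.97 × 0.995 = 7.3%. Expected: 15 × 0.073 = 1.1 subjects. P(0 of 15) = (1 − 0.073)^15 = 0.32.
- With itching and roughness: 1 − 0.99^4 × 0.97^3 × 0.995 = 12.8%. Expected: 15 × 0.128 = 1.9 subjects. P(0 of 15) = 0.13.
- Any-event incidence is therefore roughly 0 to 2 of 15. These are mostly upper values, so the true count could be lower. With two treatments per subject the same risks give 14% to 24%, or 2.1 to 3.6 of 15.

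**C. If the labels below 3% are right instead**

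- Expected with erythema: at most 15 × 0.03 = 0.45. Counting or excluding it would then matter little. The large contrast depends on the 99% figure.

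**D. How the term is used elsewhere**

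- Data Monitoring names adverse events and unexpected adverse events side by side, which suggests that expected ones are also adverse events.
- The second-treatment factors treat absence of adverse events as something to assess at one month, without saying whether resolved, expected reactions are meant.
- The 72-hour swelling limit in the treatment-visit text tells subjects when to call. It is not a definition.
- Good Clinical Practice and ICH are cited in general terms, and no definition is reproduced.

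**The case against.** Several stronger readings are tempting, and the documents do not support them.

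- **That nothing is recorded unless an event qualifies.** The Adverse Events section calls for a history, updated medications and photographs for any potential event, and the follow-up instructions say health changes are recorded. Only the two case report forms depend on the decision. A source record would therefore often exist, though not in a form that yields an incidence.
- **That the qualifying step is the only route to a form.** The treatment and follow-up instructions have no such step. They use the same undefined term, however, so they add a second trigger and do not settle the first.
- **That almost nobody could meet the second-treatment factor if expected reactions count.** That assessment is at one month, after reactions that usually fade in 24 to 72 hours, and the list is permissive. Read as status at the visit, nearly everyone could meet it. Only the ambiguity of the term remains.
- **That the low reading would be 0 of 15.** Zero is possible, but about 1 to 2 of 15 is expected at the upper listed values.

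Two further objections have force. The high reading assumes full capture, whereas the next scheduled visit after each treatment is about 30 days later and the question is open-ended. Subjects are asked to report events between visits, which helps only if they regard the reaction as an event. It can also be said that one sentence of definition would close the gap. It would settle the numerator, but it would not prompt for reactions that an open question misses, or bring in treated subjects who do not complete.

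**Conclusion.** The concern stands as a gap in definition. The plan does not define an adverse event, does not say whether expected transient reactions are included, and uses different form triggers in three places. If the 99% erythema figure is right, the same 15 subjects could give about 14 to 15 with any event or roughly 0 to 2. The low range assumes one treatment, independent risks and the upper listed values; the high range assumes that the reactions are captured. If the labels below 3% are right, the contrast largely disappears, so that conflict must be reconciled as well. Until both are settled, the secondary endpoint cannot be interpreted. The documents do not show that events go entirely unrecorded or that the second-treatment factor is unworkable. The correction should be made because it is cheap and this is the trial's only secondary endpoint.

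**What to change.** 1. **Record before classifying.** At each planned post-treatment contact, complete one fixed checklist of the local reactions named in the treatment-visit text and the Risks section. For each, note presence, approximate start and end, a mild/moderate/severe grade, and relatedness. Mark reactions that faded before the visit as recalled.
2. **Define the classes in advance.** The sponsor states which reactions, and up to what duration, count as expected. The protocol cannot supply this unaided: it gives no duration for blistering or scarring, says only that pigment change is usually temporary, and gives 7 to 10 days of downtime beside 24 to 72 hours for erythema and edema.
3. **Report two tables for all treated subjects, not only completers:** (a) expected transient reactions and (b) all other adverse events. Add this to Statistical Analysis.
4. **Use one definition and one form trigger** in the treatment-visit, follow-up and Adverse Events text, and say who makes the decision.
5. **Reconcile** the 99% and 90% figures with the labels below 3%, and state what adverse events means in the second-treatment factors. The sponsor and investigator should settle the content of that clinical rule.

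The cost is one checklist page, a few sentences of text and a few minutes per visit. The reported reaction rate will look higher, and short-lived reactions will still rest partly on recall.

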Study Procedures		Visit 1 Screening (Day -45 to 0)	Visit 2 Treatment #1 (Day 0)	Visit 3 Follow-Up #1 PI Assessment (Day 30)	Visit 4 Treatment #2 (Day 45)	Visit 5 Follow-Up #2 Tx2 1M (Day 75)	Visit 6 Follow-Up #3 Tx2 3M (Day 135)
Demographic & Eligibility	Informed Consent ; Eligibility Criteria Medical History & Demographics	X					
Safety Assessments	Adverse Events; Concomitant Medications		X	X*	X	X	X
Study Intervention	BBL /MOXI/ Halo		X		X		
Assessments	Standard Photography; VISIA Imaging/Analysis	X				X	X
Evaluations	Global Aesthetic Improvement Scale						X

*Visit 3 determine whether patient is candidate for second treatment.

Study Visits

Pre-Study Procedures

Prior to the start of the study, potential subjects will be screened for eligibility requirements via chart review on EPIC. Prospective subjects will be informed of study details and study visit instructions as detailed in section 6. An appointment to visit the clinic for an official screening visit will be scheduled if interest is demonstrated. Additionally, if subjects express an interest in the procedure during a clinic appointment with [name], he may discuss the study with them and assess the treatment area. If a subject is deemed a good candidate, they will be connected to a research coordinator to answer any further questions and provide consent.

Visit 1: Screening (Day -45 to 0)

The purpose of the study, eligibility criteria and potential risks will be discussed with the potential subject. All interested candidates will be given an IRB approved Informed Consent Form (ICF) as detailed in section 5.2, with adequate time for review. The Investigator and/or designee will address questions and/or concerns raised by the subject. Those subjects who elect to participate will sign the consent form prior to any study procedures. The subject will receive a signed copy of their ICF and the original will be kept in the study file. Subjects will then be screened to ensure they meet all study criteria. The following is a complete list of the screening and enrollment activities to be performed:

1. Obtain informed consent and HIPAA authorization.
2. Assign a screening number to candidate subjects that sign the initial paperwork.
3. Collect a brief medical history including current medications, skin type, allergies, major conditions, or illnesses, etc. and assess if subjects meet eligibility criteria.

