Subjects will be asked about any adverse events throughout the study. Subjects will be asked to contact the Investigator if adverse events develop between visits. If necessary, an unscheduled visit will be arranged so that the Investigator can clinically evaluate and photograph these findings.

Procedures to Maintain Confidentiality

All study records and information will be identified by the subject number. All subject identifiers will be removed from all documents. The link between subject name and study ID number will be kept in separate password-protected files. Documents containing identifying information will be kept in locked files in the research staffs' locked office. All electronic study data will be password protected with access limited to members of the research team. No direct identifying information will be shared with any outside entities. Electronic data (electronic data entry - Case Report Forms) will be password protected.

Photographs of subject's faces will be taken at enrollment, treatment, and follow-up visits. These photographs will be identified by subject numbers. Subject confidentiality will be protected to the greatest extent possible

This study will be performed in accordance with Health Insurance Portability and Accountability Act. These guidelines will be followed specifically with regard to the privacy and confidentiality of patient care and study records. Personnel

associated with Investigator's office, the U.S. Food and Drug Administration (FDA) and the governing Institutional Review Board, have the right to review the data, including photographs, collected during this study.

Statistical Analysis

The per-protocol (PP) population will be the primary population for all statistical analyses. The PP population will include all subjects who received treatment and completed the study in general accordance with the protocol. Only the data of completing subjects will be analyzed.

This study will include descriptive statistics and change from baseline analysis.

The primary outcome of effectiveness will be a paired comparison of baseline to all applicable post-baseline time points for data obtained from VISIA Imaging Analysis results.

A descriptive statistical summary will be provided the VISIA Imaging Analysis. The descriptive statistical summary includes the number of observations (N), mean, median, and standard deviation (SD), minimum (MIN) and maximum (MAX) values at all applicable time points.

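### The completers-only rule has no safety exception: read literally, treated subjects who leave early fall out of any analysed adverse-event incidence and, as a smaller point, usable 1-month VISIA readings are discarded

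*Combined protocol and SAP*

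**What the plan says.** The Statistical Analysis section opens with the population: "The per-protocol (PP) population will be the primary population for all statistical analyses". It defines that population: "The PP population will include all subjects who received treatment and completed the study in general accordance with the protocol". It then adds, without qualification, "Only the data of completing subjects will be analyzed". No safety, all-treated or intention-to-treat set is defined anywhere in the document, and there is no missing-data rule.

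The only secondary endpoint is safety: "Monitor incidence, severity and relatedness of adverse events throughout the study". Under Adverse Events and Data Monitoring, subjects are asked about events at each visit, each event has its own case report form, events persisting at study end are followed, and the investigator monitors event patterns and attrition. None of this is limited to completers. The Statistical Analysis section describes no adverse-event summary and gives no denominator for one.

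For efficacy, the main VISIA analysis "will be a paired comparison of baseline to all applicable post-baseline time points". VISIA is scheduled at 1 and 3 months after the final treatment. A repeated-measures ANOVA is planned, with pairwise tests if it detects differences. The study is uncontrolled and "designed to follow up to 15 consenting subjects".

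**The concern.** An incidence needs a numerator and a denominator. The only population rule that the plan offers for adverse events is completers-only, so a treated subject who leaves early contributes to neither. If leaving is related to harm, the analysed incidence is too low. If the leavers had no event, it is too high. With at most 15 subjects and no control group, one exclusion can remove the only case of an uncommon event from the analysed figure, though its case report form remains.

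For VISIA, the same rule conflicts in spirit with a plan that compares baseline with each later time point separately. A subject with baseline and 1-month readings has everything the 1-month comparison needs, yet is dropped for missing a later visit. The 1-month result loses precision and can shift in either direction. That loss is avoidable, because the reading exists.

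**Working it through.** The plan gives no power calculation, dropout rate, adverse-event rate for the combined treatment or VISIA standard deviation, so there is no figure of its own to reproduce. The first two steps are textual and the rest are illustrations.

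**1. Who is excluded from what.** The document does not define completion. I take it to mean attending the 3-month visit after the final treatment, since the Follow Up Visits section requires at least the 1-month and 3-month visits.

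| Treated subject | In per-protocol set? | Ruled out by the completers-only sentence? |
|---|---|---|
| Completed, in general accordance | Yes | No |
| Completed, not in general accordance | No | No |
| Left early | No | Yes |

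Only the third row is shut out of every analysis.

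**2. Which VISIA readings are lost.** The Study Timeline tables schedule post-baseline VISIA at Days 30 and 90 (single treatment) and Days 75 and 135 (two treatments). The readings at stake are therefore Day 30 or Day 75 in a subject who then misses Day 90 or Day 135. A two-treatment subject who leaves before Day 75 has no scheduled post-baseline reading to discard.

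**3. Adverse-event incidence.** Assume that all 15 are treated. The intervals are exact (Clopper-Pearson) 95%.
- All treated, one case: 1/15 = 6.7%. Lower limit 1 − 0.975^(1/15) = 0.0017. Upper limit, the 0.975 quantile of Beta(2, 14), = 0.3195. Interval 0.2% to 31.9%.
- That case leaves: 0/14 = 0%. Upper limit 1 − 0.025^(1/14) = 0.2316, or 23.2%.
- The opposite direction, with two leavers who had no event and the case staying: 1/13 = 7.7% against 1/15 = 6.7%.

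**4. Month-1 VISIA mean.** Assume 15 subjects whose change scores are normal with SD 1, and that k = 1, 2 or 3 leave after month 1. Leavers are chosen on month-1 change plus independent noise of equal variance, so the selection score correlates 1/√2 = 0.707 with month-1 change. A simulation of 100,000 runs gave shifts in the completers' month-1 mean of 0.09, 0.16 and 0.23 SD, upward if poor responders leave and downward if good responders leave. A direct check uses the expected three largest of 15 standard normal values: 1.736, 1.248 and 0.948.
- k = 1: 0.707 × 1.736 / 14 = 0.09
- k = 2: 0.707 × (1.736 + 1.248) / 13 = 0.16
- k = 3: 0.707 × (1.736 + 1.248 + 0.948) / 12 = 0.23

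If leaving is random, the shift is about 0. With all available pairs, the simulated month-1 mean is within 0.001 SD of the truth.

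**5. Scale for comparison.** The 95% CI half-width for a mean change, in SD units, is t(0.975, n − 1)/√n. For n = 15 this is 2.145/√15 = 0.55, and for n = 12 it is 2.201/√12 = 0.64. Even the largest shift is well inside it.

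**The case against.** The strongest reply is that the plan describes no adverse-event analysis at all. Every method detailed in the section is of the VISIA kind (paired comparison, percent change, ANOVA), so the completers rule was probably written for efficacy and the real gap is a missing safety summary. It stands that the exclusion follows from general wording and not from an explicit safety rule. It does not remove the point: the wording covers all statistical analyses, the endpoint includes incidence, and no other population is available. Calling the per-protocol set primary hints at others, but none is named, and the completers sentence excludes any that contains leavers.

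A second reply is that the efficacy effect is small and depends on assumed dropout, and that the ANOVA in its standard form uses only subjects with every visit anyway. Both parts stand. They make this the lesser half of the point and mean that the fix must address the ANOVA too.

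A reader might infer more than the text supports:
- *That leavers' adverse events go unrecorded.* They do not. The rule limits what is analysed, and the Adverse Events and Data Monitoring provisions apply to every subject.
- *That completers judged not in general accordance also vanish from the incidence.* They are outside the primary population, but the completers-only sentence does not rule them out.
- *That a subject denied a second treatment because of an adverse event is excluded.* The table footnote reads "Visit 3 determine whether patient is candidate for second treatment", and a subject who is not a candidate can still complete on the single-treatment schedule.

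**Conclusion.** The point holds and should be fixed, with medium confidence. It is a stated rule that, followed as written, gives a worse result. The safety part is the main one: treated early leavers are excluded from any analysed adverse-event incidence. With 15 treated, losing a single case takes 6.7% to 0%. The bias can run either way and is nil if nobody leaves. The VISIA part is secondary: about 0.09 to 0.23 SD at month 1 under response-related loss of 1 to 3 of 15, and about 0 under random loss. The documents do not support a claim of serious efficacy bias. All sizes rest on assumed dropout, and the VISIA sizes also on normal changes and the assumed selection mechanism.

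**What to change.** Amend the Statistical Analysis section:

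1. Delete the completers-only sentence, and reword the sentence on the per-protocol population so that it no longer governs all statistical analyses. Deleting the first alone would leave a contradiction with the next two items.
2. Summarise adverse-event incidence, severity and relatedness in every subject who received at least one BBL/MOXI/HALO treatment, with the number treated as denominator.
3. For each VISIA comparison with baseline, use all treated subjects with a baseline reading and a reading at that visit. In the percent-change formula, take the baseline mean from those same subjects. Report per-protocol completers as a sensitivity analysis. Report the paired comparisons with baseline whatever the ANOVA shows, and state the ANOVA's N.
4. Report the number, timing and reasons of early exits.

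This needs no new data or visits. The cost is that numbers analysed may differ between visits and results may move slightly in either direction. One limit remains and should be stated: month-3 results still describe only those with a month-3 reading.
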